### **5.5.2. Clinical Laboratory Assessments and Vital Signs**

Laboratory data (hematology, serum chemistry, coagulation, FSH and urinalysis) will be converted to Système International (SI) units for reporting and processing purposes.

Descriptive summaries of absolute values of quantitative clinical laboratory results and their change from baseline values will be presented by analysis visit and treatment group. Observed values of categorical urinalysis data will be displayed with frequencies and percentages. All laboratory data will be listed for individual patients.

Treatment-emergent abnormal laboratory assessments will be based on the lab provided normal ranges. If the baseline laboratory assessment is normal and shifts to Low or High post-baseline, then the laboratory value is considered a TE abnormal laboratory value. If the baseline laboratory assessment is Low and shifts to High post-baseline or the baseline laboratory assessment is High and shifts to Low post-baseline, then the laboratory value is considered a TE abnormal laboratory

value. For each protocol specified lab test, the number and percent of patients reporting a TE abnormal lab will be reported.

For CK, Absolute Neutrophils, ALT, AST, and Bilirubin, laboratory abnormalities will be graded via the Common Terminology Criteria for Adverse Event (CTCAE) version 5.0. A summary of treatment-emergent laboratory toxicities for the indicated laboratory results by maximum CTCAE toxicity grades will be reported.

All laboratory summaries will be limited to the tests specified in the protocol.

Descriptive summaries of vital signs, weight, and BMI and their change from baseline will be presented by study visit and treatment group and all vital signs will be listed.

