5.1 Inclusion Criteria

Patients must meet the following criteria to be eligible for participation in the study:

1. Able to comprehend and be willing to sign the IRB-approved patient ICF prior to administration of any study-related procedures.
2. Patient with HS for at least 1 year (365 days) prior to Baseline visit; duration of disease as determined via Investigator review of patient medical history.
3. Patient must have stable HS for at least 60 days prior to Screening visit and at Baseline visit as determined via Investigator review of patient medical history.
4. Total AN count of ≥ 5 at Baseline visit. Abscesses and nodules must have the following signs of inflammation. (Inflammatory nodules should be raised):
 - a. Clinical evidence of erythema and/or warmth.
 - b. Clinical evidence of pain/tenderness.
5. Has HS lesions present in at least 2 distinct anatomical areas at Screening and Baseline. (Bilateral involvement of the same area counts as 2 areas, eg, involvement of right and left axilla.)
6. Draining fistula count of ≤ 20 at Baseline visit.
7. Male or nonpregnant, nonbreastfeeding female patients between 18 and 70 years of age, inclusive, at the time of signing the ICF.
 - a. Heterosexually active female patients who are of childbearing potential must use 2 methods of highly effective contraception, 1 of which must be a physical barrier, for the duration of the study and for 30 days after the last dose (see [Appendix 6](#)).
 - b. Heterosexually active male patients of childbearing potential with a female partner of childbearing potential must agree to use a condom plus another highly effective form of birth control for the duration of the study and for 90 days after the last dose (see [Appendix 6](#)).
8. Female patients of childbearing potential must have a negative serum pregnancy test at Screening and a negative urine pregnancy test prior to dosing on Day 1.
9. Screening laboratory evaluations (hematology, chemistry, coagulation, and urinalysis) must fall within the normal range of the central laboratory's reference ranges unless the results have been determined by the Investigator to not be clinically significant.
10. No COVID-19 vaccination or booster within the 4 weeks prior to randomization. Note: COVID vaccination is highly encouraged but not required.

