8.2.4 Clinical Safety Laboratory Assessments

See [Appendix 3](#) for the list of clinical laboratory tests to be performed and the SoA ([Table 1](#)) for the timing and frequency.

The Investigator must review the laboratory report, document this review, and record any clinically relevant changes occurring during the study in the AE Section of the eCRF. The laboratory reports must be filed with the source documents. Clinically significant abnormal laboratory findings are those that are not associated with the underlying disease, unless judged by the Investigator to be more severe than expected for the patient's condition.

See [Section 7.0](#) for discontinuation criteria based on abnormal liver function tests, neutrophil values, CK values, or positive SARS-CoV-2 test.

All laboratory tests with values considered clinically significantly abnormal during participation in the study or within 30 days (+7 days) after the last dose of study treatment should be repeated until the values return to normal or Baseline or are no longer considered clinically significant by the Investigator or Medical Monitor.

- If such values do not return to normal/Baseline within a period of time judged reasonable by the Investigator, the etiology should be identified and the Medical Monitor notified.
- All protocol-required laboratory assessments, as defined in [Appendix 3](#), must be conducted in accordance with the Laboratory Manual and the SoA ([Table 1](#)).
- If laboratory values from non-protocol specified laboratory assessments performed at the institution's local laboratory require a change in patient management or are considered clinically significant by the Investigator (eg, SAE or AE), then the results must be recorded in the eCRF.
- Serum potassium levels < 3.8 mmol/L will be treated and repeated as will serum magnesium levels < LLN.

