Dermatology Life Quality Index (DLQI)

The DLQI is calculated by summing the score of each question resulting in a maximum of 30 and a minimum of 0. The higher the score, the more quality of life is impaired. If one question is unanswered, this is allocated a score of 0 for the purpose of summing to the DLQI score. If two or more questions are unanswered, the questionnaire is not scored.

Each question is answered on a Likert scale: Very much=scored 3, A lot=scored 2, A little= scored 1, Not at all= scored 0, Not relevant=scored 0, Question Not Answered=0. Question 7 is asked in two parts. The first part asks if the skin disease has ‘prevented you from working or studying’. If skin disease has prevented working or studying, then Question 7 is scored 3. If working or studying are not relevant, the response is Not relevant and scored 0. If the answer is No, then Question 7 is scored based on the second part of the question as to ‘How much has your skin been a problem at work or studying’: ‘A lot’(scored 2), ‘A little’ (scored 1) or ‘Not at all’ (scored 0).

Treatment-Emergent Adverse Event (TEAE)

TEAEs are defined as AEs with an onset date on or after the date of first administration of study drug and before the date of last administration of study drug + 30 days.

Treatment-Emergent Laboratory Abnormalities

A treatment-emergent laboratory abnormality is defined as a result in which the baseline value is within normal laboratory limits and the post-baseline value is outside normal laboratory limits. If the relevant baseline assessment is missing, then any post-baseline value outside normal laboratory limits will be considered a treatment-emergent value.

Treatment-emergent Laboratory Toxicity

A treatment-emergent laboratory toxicity is defined as an increase of at least one toxicity grade from the baseline assessment at any post baseline visit. If the relevant baseline assessment is missing, then any graded abnormality (i.e., at least Grade 1) is considered to be treatment-emergent.

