## **5. STATISTICAL METHODS**

Descriptive statistical methods will be used to summarize the data from this study, with hypothesis testing performed for the primary and secondary efficacy endpoints. Unless stated otherwise, the term “descriptive statistics” refers to number of patients, mean, median, standard deviation, minimum, and maximum for continuous data, and frequencies and percentages for categorical data. For categorical variables, the denominator of percentages will be the number of patients with a

---

non-missing value at the visit and/or the scheduled time point. If a different denominator is used, this will be identified in the summary table.

All data collected during the study will be included in data listings. Unless otherwise noted, the data will be sorted first by treatment group, subject number, and then by date within each subject number. Assessments indicated as 'Not Done' will not be included in the listings.

The term 'treatment group' refers to all patients on the same dosing regimen. There will be two treatment groups in this study: Placebo BID and ATI-450 50mg BID.

All statistical testing will be one-sided and will be performed using a significance (alpha) level of 0.05 unless otherwise stated. P-values will be presented to three decimal places. For the efficacy endpoints, the ATI-450 treatment group will be tested versus Placebo via statistical inference.

The statistical analyses will be conducted with the SAS® software package version 9.4 or higher. All analyses will be subject to formal verification procedures. Specifically, results will be independently verified by a second programmer or statistician prior to issuance of the draft statistical report. All documents will be reviewed by the lead statistician to ensure accuracy and consistency.

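### The treatment-emergent laboratory tables pool Low and High shifts into one count per test and do not exclude patients already out of range, which dilutes a one-directional drug effect

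*SAP*

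**What the plan says.** SAP 5.5.2 defines the event in two steps. For a normal Baseline: "If the baseline laboratory assessment is normal and shifts to Low or High post-baseline, then the laboratory value is considered a TE abnormal laboratory". For an abnormal Baseline, a crossing to the other side also counts: "If the baseline laboratory assessment is Low and shifts to High post-baseline or the baseline laboratory assessment is High and shifts to Low post-baseline". The output is then a single figure per test: "For each protocol specified lab test, the number and percent of patients reporting a TE abnormal lab will be reported". Tables 14.3.4.2.1 (hematology and coagulation), 14.3.4.2.2 (chemistry) and 14.3.4.2.3 (urinalysis) are titled by analysis visit, and none names a direction. The output list contains no shift table.

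SAP 3.3.8 has its own definition, which requires that the "baseline value is within normal laboratory limits and the post-baseline value is outside normal laboratory limits". It is also direction-free, but it differs from 5.5.2 in two ways. It does not count Low-to-High or High-to-Low crossings, and it has a rule for a missing Baseline, which 5.5.2 lacks.

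On denominators, SAP section 5 begins its general rule "For categorical variables, the denominator of percentages will be the number of patients with a" and goes on to specify a non-missing value at the visit or time point. A table may use another denominator if it says so. Nothing in 5.5.2 restricts the denominator to patients at risk of the shift.

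CTCAE grading covers CK, neutrophils, ALT, AST and bilirubin only, and the laboratory plots cover the same five.

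**The concern.** Laboratory abnormalities are among the secondary endpoints in Protocol section 3.0, and these tables are the main planned tabulation of their incidence. Several of the protocol's own laboratory limits run in one direction. Exclusion 8 sets floors for white cells, neutrophils, lymphocytes, platelets and haemoglobin, and exclusion 27 does so for potassium and magnesium. During the study, "Serum potassium levels < 3.8 mmol/L will be treated and repeated as will serum magnesium levels < LLN". Of these tests, only neutrophils are CTCAE-graded.

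A count that adds Low and High answers a different question from the one these limits raise. High values unrelated to treatment add noise to a drug-related fall. If they also become rarer on ATI-450, they offset it.

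The denominator adds a smaller problem. Inclusion criterion 9 admits patients with out-of-range screening results "unless the results have been determined by the Investigator to not be clinically significant". A patient who is Low at Baseline cannot have a new Low shift, but is still counted in the percentage.

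**Working it through.** **Plan figures.** The documents give no laboratory shift rates, so there is no plan figure to reproduce on this point. The only input carried over is 45 patients per arm (SAP 1.1 and 3.1). The power stated alongside it, 90.3%, reproduces. The noncentrality is 2.25 / (3.6 × √(2/45)) = 2.96, and a one-sided 0.05 t test with 88 df gives 90.27%. Nothing here depends on that figure.

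**Set-up.** Take one analysis visit with a value from all 45 patients in each arm. Each patient contributes one value, so Low and High exclude each other and the pooled rate is their sum. All rates below are assumptions. No laboratory test is planned, so the ratio z of the difference to its standard error (SE) is only a yardstick, and it is rough at rates as small as 2%.

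SE = √{[p₀(1 − p₀) + p₁(1 − p₁)] / 45}, with p₀ for placebo and p₁ for ATI-450.

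Low alone, 2% vs 15%: SE = √[(0.0196 + 0.1275)/45] = 0.057, so z = 0.13/0.057 = 2.3.

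| High shifts, placebo vs ATI-450 | Pooled, placebo vs ATI-450 | SE | z |
|---|---|---|---|
| 0% vs 0% | 2% vs 15% | 0.057 | 2.3 |
| 2% vs 2% | 4% vs 17% | √[(0.0384 + 0.1411)/45] = 0.063 | 2.1 |
| 5% vs 5% | 7% vs 20% | √[(0.0651 + 0.1600)/45] = 0.071 | 1.8 |
| 10% vs 10% | 12% vs 25% | √[(0.1056 + 0.1875)/45] = 0.081 | 1.6 |
| 15% vs 7% | 17% vs 22% | √[(0.1411 + 0.1716)/45] = 0.083 | 0.6 |
| 15% vs 2% | 17% vs 17% | – | 0 |

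Equal High rates leave the 13-point difference intact and only widen its error. The difference itself shrinks only when High shifts are rarer on ATI-450.

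**The same in whole patients** (assumed counts, one-sided Fisher p as yardstick). Low shifts are 8/45 (17.8%) on ATI-450 and 2/45 (4.4%) on placebo, p = 0.045.
- High 2 vs 2: pooled 10/45 (22.2%) vs 4/45 (8.9%), p = 0.07.
- High 1 on ATI-450 vs 5 on placebo: pooled 9/45 (20.0%) vs 7/45 (15.6%), p = 0.39.
- High 1 on ATI-450 vs 7 on placebo: pooled 9/45 vs 9/45, no difference.

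**Denominator.** Suppose 8 new Low shifts occur among 45 patients. With 0, 5, 10 or 15 patients already Low at Baseline, the at-risk incidence is 8/45 = 17.8%, 8/40 = 20.0%, 8/35 = 22.9% or 8/30 = 26.7%. The rule in SAP section 5 prints 17.8% each time.

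**The two definitions side by side.**

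| Baseline → post-baseline | SAP 3.3.8 | SAP 5.5.2 |
|---|---|---|
| Normal → Low or High | counts | counts |
| Low → High, High → Low | does not count | counts |
| Missing → Low or High | counts | not addressed |

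Two programmers working from different sections could produce different counts from the same data.

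**The case against.** The strongest reply is that this concerns one set of descriptive tables, and direction is kept elsewhere. SAP 5.5.2 summarizes values and change from baseline for every quantitative test by visit and arm. Under SAP section 5, those summaries include the median, minimum and maximum. All laboratory data are listed, with a separate listing of abnormalities. Protocol 8.2.4 has clinically relevant changes recorded as adverse events, which SAP 5.5.1 tabulates. Under Protocol 9.6 an independent board reviews unblinded safety data. All of this stands, and it limits the point. None of these outputs gives an incidence of out-of-range values by direction and arm, however. A mean can miss a few patients, a minimum shows one patient, and a listing gives no rate.

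Three stronger readings are tempting, and the documents do not support them.
- A reader might infer that opposite shifts will cancel a harm. The documents describe a neutrophil and lymphocyte response in the skin. They do not say that HS raises circulating lymphocytes or platelets, and nothing suggests inflammation-driven High potassium. Cancellation is arithmetically possible, not shown to be likely.
- A reader might infer that the percentages are taken over all patients. The rule is patients with a non-missing value at the visit.
- A reader might treat every patient abnormal at Baseline as out of risk. Under 5.5.2 such a patient can still count by crossing to the opposite side, so only the direction already occupied is closed.

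Two more limits stand. Table shells and the laboratory test list (Protocol Appendix 3) are not in the documents reviewed. The shells may already split by direction, and it cannot be confirmed that each test named here is in the tables. Also, the protocol does not say that potassium of 3.8 mmol/L is the laboratory's lower limit, so a row based on reference ranges may not match that threshold.

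**Conclusion.** The point holds as a cheap improvement. As written, the SAP pools Low and High shifts, does not remove patients already out of range in the direction of interest, and carries two definitions that disagree. For tests outside the five graded ones (for example platelets, lymphocytes, haemoglobin, potassium and magnesium, if they are in the test list), no laboratory table gives an incidence by direction.

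Under the assumed rates, the cost is dilution from 2.3 to between 2.1 and 1.6 standard errors when High shifts run at 2% to 10% in both arms. There is no loss if High values do not occur. Masking requires an offsetting fall in High shifts, for which the documents give no rates. The effect is confined to Tables 14.3.4.2.1 and 14.3.4.2.2. It does not mean that the safety evaluation as a whole would miss a signal, and no sample-size or efficacy figure changes.

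**What to change.** Replace the definitions in SAP 3.3.8 and 5.5.2 with one rule, applied to each quantitative test in Tables 14.3.4.2.1 and 14.3.4.2.2:
- *TE Low*: Baseline not Low, or missing, and post-baseline Low.
- *TE High*: Baseline not High, or missing, and post-baseline High.

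Give the two as separate rows, at each analysis visit and once for any post-baseline value. At a visit, the denominator is the patients at risk for that direction (Baseline not already Low, or not already High, or missing) who have a value at that visit. For the overall row, it is the patients at risk with at least one post-baseline value. State the denominator in the table, as SAP section 5 already requires when it departs from the default. A patient may appear in both overall rows, so those rows should not be added.

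The single rule counts Low-to-High and High-to-Low crossings and covers a missing Baseline, which settles both conflicts. If the shells already split by direction, the SAP need only say so and state the denominators.

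The cost is a change of SAP wording and longer tables. It needs no new data and no protocol amendment.

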#### **5.5.3. Other Safety Analyses**

ECG measurements will include heart rate, QT interval, Fredericia-corrected QT interval (QTcF), PR interval, and QRS interval. Triplicate ECG values will be obtained at each time point. Summary tables will present the average of the triplicate ECG results. ECG results and their change from baseline values will be summarized descriptively by treatment group at each scheduled evaluation and all ECG data will be listed. Proportion of patients with abnormal ECG interpretations will be summarized at each study visit and by treatment group for both investigator and central interpretation. Proportion of patients who meet each of the following criteria based on triplicate averages from International Conference on Harmonization Guideline E14 “Clinical Evaluation of QT/QTc Interval Prolongation and Proarrhythmic Potential for Non-Antiarrhythmic Drugs” (October 2005) for QT and corrected QT intervals will be summarized across treatment groups:

- QTcF >450 msec
- QTcF >480 msec
- QTcF >500 msec
- QTcF increases from baseline by >30 msec
- QTcF increases from baseline by >60 msec

The above summaries will be repeated for QT.

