3.0 OBJECTIVES AND ENDPOINTS

Table 2 Study Objectives and Endpoints

Objectives	Endpoints
Primary	

 To assess the efficacy of ATI-450 in patients with moderate to severe HS 	
 Change from Baseline in inflammatory nodule/abscess count at Week 12
Secondary	
 Percentage of patients achieving HiSCR at Week 12. 
HiSCR is defined as at least a 50% reduction from Baseline in the total abscess and inflammatory nodule (AN) count, with no increase in abscess or draining fistula counts.
 
 Change from Baseline in IHS-4 over time for the 12-week treatment period. Percentage of patients achieving at least a 30% reduction and at least 1 unit reduction from Baseline in the numerical rating scale (NRS30) in Patient's Global Assessment of Skin Pain at Week 12 among patients with Baseline NRS ≥ 3. 
NRS30 is evaluated based on worst skin pain in a 24-hour recall period (maximal daily pain).
 
 Change from Baseline in Hidradenitis Suppurativa-Physician Global Assessment (HS-PGA) over time for the 12-week treatment period. Change from Baseline in Dermatology Life Quality Index (DLQI) over time for the 12-week treatment period. 
The DLQI is a 10-item validated questionnaire used to assess the impact of HS disease symptoms and treatment on quality of life (QoL). It consists of 10 questions evaluating impact of skin diseases on different aspects of a patient's QoL over the prior week, including symptoms and feelings, daily activities, leisure, work or school, personal relationships, and the side effects of treatment.

Objectives	Endpoints
Secondary (continued)	
	
 Change from Baseline in Hurley Stage over time for the 12-week treatment period. Incidence of adverse events (AEs), serious AEs (SAEs), laboratory value abnormalities, electrocardiogram (ECG) abnormalities, vital signs abnormalities

 To assess the PK of ATI-450 in patients with moderate to severe HS 	
 Trough ATI-450 and metabolite (CDD-2164) concentrations at clinic visits. On Day 1, 8, and 85 trough and 2-hour post dose will be collected.
Exploratory	

 To assess the pharmacodynamics (PD) of ATI-450 in patients with moderate to severe HS 	 

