10. Clinically significant abnormal findings other than HS from PE conducted at Screening visit (Visit 1) and at Baseline visit (Visit 2) that may affect the interpretation of study data or the safety of the patient's participation in the study, per the judgment of the Investigator.
11. Clinically important history of a medical disorder that would compromise patient safety or data quality, per judgment of the Investigator.
12. Blood pressure levels (in semi-supine position after at least 5 minutes rest): <90 mmHg or >150 mmHg for systolic BP or <40 mmHg or >90 mmHg for diastolic BP.
13. Patient has experience with >2 biologics, >1 JAK inhibitor, or a combination of 1 biologic experience and 1 JAK inhibitor.

15. Are currently receiving corticosteroids at doses greater than 10 mg per day of prednisone (or equivalent) or have been receiving an unstable dosing regimen of corticosteroids within 2 weeks of the Screening visit.
16. Have been using prescription topical therapies for treatment of HS within 14 days prior to Baseline visit.
17. Oral or topical tetracycline class antibiotics for treatment of HS are allowable if patient is on a stable dose for 4 weeks prior to Baseline and willing and able to maintain the stable dose for duration of study.

[REDACTED]

[REDACTED]

[REDACTED]

20. Patients with history of stroke.

21. Significant active cardiac disease, in the past 6 months, that would affect interpretation of study data or the safety of the patient's participation in the study, per judgment of the Investigator. This includes myocardial infarction or unstable angina, acute coronary syndrome, or heart failure with New York Heart Association Class II, III or IV symptoms. In addition, patients with a personal or family history of congenital long QT syndrome, Torsades de Pointes, sustained or symptomatic VT, or unexpected sudden cardiac death.

22. Patients with any of the following Baseline predose ECG findings:

- Mean QTcF >450 msec as averaged on triplicate ECG;
- ECG or historical evidence of the Wolff-Parkinson-White Syndrome (unless ablated);
- If atrial fibrillation or flutter is present, the mean ventricular response must be < 90 BPM and the patient must be anticoagulated according to national guidelines; and/or
- Any other finding that is considered clinically significant.

23. Any dermatologic surgery or procedure in the past 90 days prior to Screening.

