### **3.3.9. Presentations by Study Visit**

Scheduled and unscheduled assessments collected from Visit 1 through Visit 8 for all efficacy assessments and safety assessments (labs, vital signs, and ECG) will be assigned to an analysis visit window using the study day ranges described in [Table 1](#) and [Table 2](#). All study days up to and

---

including Day 1 are in the baseline-eligible analysis visit window. The last non-missing assessment in the baseline-eligible analysis visit window will be used in any summaries that present the baseline results with the exception of ECG interpretation where the best result from the triplicate values will be chosen. Day 1 post-dose ECG, PK and vital signs assessments will be analyzed as collected. Day 8 ECG assessments, Day 8 and 85 PK assessments, and Day 8, 15, 29, 43, 57 and 85 vital sign assessments will be windowed per Table 2, then each time point will be analyzed as collected. For all other assessments, for post-baseline analysis windows, if multiple assessments occur within a given analysis visit window, the result closest to the target study day, regardless of whether scheduled or unscheduled, will be used for summary presentations. If two measurements have the same distance to the target study day, the first assessment will be used in the summary presentations with the exception of ECG interpretation where the worst result from the triplicate values for the given visit and timepoint will be used. All assessments will be presented in the listings. In addition to the analysis visits indicated in Table 1 and Table 2, for patients who prematurely discontinue the study, data collected during the withdrawal visit will be used as an EOS assessment for these patients. The EOS assessment will be included in safety analyses.

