## **Section 14.3 Safety**

Table 14.3.1.1 Overall Summary of Adverse Events, Safety Population

Table 14.3.1.2 Treatment-Emergent Adverse Events by System Organ Classification, Preferred Term and Greatest Severity, Safety Population

Table 14.3.1.3 Treatment-Emergent Adverse Events by System Organ Classification and Preferred Term, Safety Population

Table 14.3.1.4 Treatment-Emergent Serious Adverse Events by SOC and PT, Safety Population

Table 14.3.1.5 Treatment-Emergent Adverse Events Related to Study Drug by SOC and PT, Safety Population

Table 14.3.1.6 Treatment-Emergent Adverse Events Leading to Discontinuation of Study Drug by SOC and PT, Safety Population

Table 14.3.1.7 Study Drug Related Treatment-Emergent Adverse Events Leading to Discontinuation of Study Drug by SOC and PT, Safety Population

Table 14.3.1.8 Adverse Events of Special Interest (AESI) by SOC and PT, Safety Population

Table 14.3.1.9 Summary of Most Frequent Treatment Emergent Adverse Events by Preferred Term, Safety Population

Table 14.3.4.1.1 Summary of Hematology and Coagulation Results and Change from Baseline by Analysis Visit, Safety Population

Table 14.3.4.1.2 Summary of Serum Chemistry Results and Change from Baseline by Analysis Visit, Safety Population

Table 14.3.4.1.3 Summary of Urinalysis Results and Change from Baseline by Analysis Visit, Safety Population

Table 14.3.4.2.1 Summary of Treatment-Emergent Abnormal Hematology and Coagulation by Analysis Visit Safety Population

Table 14.3.4.2.2 Summary of Treatment-Emergent Abnormal Serum Chemistry by Analysis Visit, Safety Population

Table 14.3.4.2.3 Summary of Treatment-Emergent Abnormal Urinalysis by Analysis Visit, Safety Population

Table 14.3.4.4 Summary of Laboratory Results by CTCAE Toxicity Grades for CK, Absolute Neutrophils, ALT, AST, and Bilirubin, Safety Population

---

Table 14.3.5.1 Summary of Vital Signs and Change from Baseline by Analysis Visit, Safety Population

Table 14.3.5.2.1 Summary of ECG Results and Change from Baseline by Analysis Visit, Safety Population

Table 14.3.5.2.2.1 Proportion of Patients with Abnormal Investigator ECG Interpretations by Analysis Visit, Safety Population

Table 14.3.5.2.2.2 Proportion of Patients with Abnormal Central ECG Interpretations by Analysis Visit, Safety Population

Table 14.3.5.2.3 Proportion of Patients with Noteworthy QT Changes by Analysis Visit, Safety Population

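### Abnormal ECG interpretations are tabulated only as by-visit prevalence, so new ones not reported as adverse events are never shown separately from those present before dosing

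*SAP*

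**What the plan says.** Protocol Section 3.0 (Table 2) gives the secondary safety endpoint as an incidence: "Incidence of adverse events (AEs), serious AEs (SAEs), laboratory value abnormalities, electrocardiogram (ECG) abnormalities, vital signs abnormalities". The synopsis says the same.

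SAP Section 5.5.3 plans, for ECG interpretations: "Proportion of patients with abnormal ECG interpretations will be summarized at each study visit and by treatment group for both investigator and central interpretation". The table list in SAP Section 9 matches this with two tables, one per reader. For the investigator reading the title is "Proportion of Patients with Abnormal Investigator ECG Interpretations by Analysis Visit, Safety Population" (number 14.3.5.2.2.1). The central reading has a counterpart of the same layout, number 14.3.5.2.2.2, under the title "Proportion of Patients with Abnormal Central ECG Interpretations by Analysis Visit, Safety Population".

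SAP Section 3.3.9 sets how one interpretation is chosen from each triplicate. At Baseline there is a departure from the usual rule, "with the exception of ECG interpretation where the best result from the triplicate values will be chosen". After Baseline there is another, "with the exception of ECG interpretation where the worst result from the triplicate values for the given visit and timepoint will be used".

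SAP Section 3.3.8 defines treatment-emergent adverse events, laboratory abnormalities and laboratory toxicities. It has no equivalent for ECG interpretations.

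**The concern.** A prevalence at each visit is not an incidence. A patient whose ECG was abnormal before dosing and stays so is counted at each of the six later treatment-period visits (Days 8, 15, 29, 43, 57 and 85), in the same cell as a patient whose ECG has just become abnormal. The two cannot be told apart in the table.

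Such patients can be enrolled. Exclusion 22 in Protocol Section 5.2 admits rate-controlled arrhythmia ("If atrial fibrillation or flutter is present, the mean ventricular response must be < 90 BPM", with anticoagulation) and removes other Baseline findings only if they are judged clinically significant.

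At stake is whether a modest excess of new rhythm, conduction or morphology findings on ATI-450 would be visible in the tables. ECG safety matters in this trial: triplicate tracings are taken at every visit to Day 85, all are read centrally, and the protocol has QTcF criteria for interrupting dosing.

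**Working it through.** **Step 1. What each planned output captures.** The documents contain no ECG abnormality rate, so there is no figure of the plan's own to reproduce. The first check sets the outputs side by side.

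| Output | Source | Relates to Baseline? | Once per patient? |
|---|---|---|---|
| Abnormal interpretation, each reader | SAP 5.5.3; Tables 14.3.5.2.2.1 and 14.3.5.2.2.2 | No | No, by visit |
| QT and QTcF increase >30 and >60 msec | SAP 5.5.3 | Yes | No, by visit |
| QTcF >450, >480, >500 msec | SAP 5.5.3 | In effect yes, as Baseline mean QTcF >450 is excluded | No, by visit |
| Heart rate, PR, QRS, QT, QTcF values | SAP 5.5.3 | Yes, change from Baseline | Descriptive only |
| Clinically significant ECG findings, as TEAEs | Protocol 8.2.3; SAP 5.5.1 | Yes, by onset date | Yes |
| QTcF >500 or change >60 msec, as AESI | SAP 5.5.1; Table 14.3.1.8 | Partly | Yes |
| Laboratory abnormalities | SAP 3.3.8, 5.5.2 | Yes, treatment-emergent | Number and percent of patients |

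What remains uncovered is a new abnormal interpretation that is not a QT or QTcF finding and was not reported as an adverse event. Adverse event reporting depends on a judgement of clinical significance, so the gap is mainly non-significant findings and findings of the central reader.

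**Step 2. Dilution.** Let *b* be the proportion persistently abnormal from Baseline and *i* the proportion newly abnormal among those normal at Baseline. Then visit prevalence = *b* + (1 − *b*)*i*, and the between-arm difference in prevalence = (1 − *b*)(*i*₁ − *i*₀). Assume *i*₁ = 15% on ATI-450 and *i*₀ = 3% on placebo, a difference of 12 points, with 45 per arm (SAP 1.1).

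| *b* (assumed) | Placebo prevalence | ATI-450 prevalence | Difference (points) | SE (points) | Difference/SE |
|---|---|---|---|---|---|
| 20% | 22.4% | 32.0% | 9.6 | 9.3 | 1.03 |
| 30% | 32.1% | 40.5% | 8.4 | 10.1 | 0.83 |
| 40% | 41.8% | 49.0% | 7.2 | 10.5 | 0.69 |

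Here SE = √{[p₁(1 − p₁) + p₀(1 − p₀)]/45}. Among patients at risk (36, 31.5 and 27 expected per arm), the difference stays at 12 points with SE = √{(0.03×0.97 + 0.15×0.85)/n} = 6.6, 7.1 and 7.6 points, so the ratios are 1.82, 1.70 and 1.58. In simulated trials under these assumptions, the prevalence comparison pointed the wrong way or tied in 18% to 28% of trials. The at-risk comparison did so in 3% to 6%.

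A second set of assumed rates, 20% against 5% new onset (ratio 4.0), gives prevalence ratios of 1.93, 1.50, 1.31 and 1.21 for *b* = 10%, 20%, 30% and 40%. If *i*₁ = *i*₀, the expected difference is zero for every *b*.

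**Step 3. Chance imbalance at Baseline.** SD of the between-arm difference = √[2*b*(1 − *b*)/45] = 8.4, 9.7 and 10.3 points for *b* = 20%, 30% and 40%. Multiplying by 1.645 gives ±13.9, ±15.9 and ±17.0 points as the range for 90% of trials. This is ordinary sampling error, but it enters every visit's comparison and says nothing about the drug.

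**Step 4. The triplicate rule.** Let *p* be the chance that one tracing is read as abnormal, with no drug effect and independent tracings. If the best reading is chosen, the result is abnormal with probability *p*³. If the worst is chosen, it is 1 − (1 − *p*)³. Apparent new abnormality at one visit is their combination, (1 − *p*³)[1 − (1 − *p*)³].

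| *p* (assumed) | Baseline abnormal (best) | One later visit abnormal (worst) | Apparently new |
|---|---|---|---|
| 5% | 0.01% | 14.3% | 14.3% |
| 10% | 0.1% | 27.1% | 27.1% |
| 20% | 0.8% | 48.8% | 48.4% |
| 30% | 2.7% | 65.7% | 63.9% |

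Independence is the extreme case, and correlated tracings would shrink these figures. Even so, Baseline and later proportions are not on the same footing, and a treatment-emergent count built on the stated rule would produce apparent new abnormalities in both arms.

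**The case against.** The strongest reply has four parts.

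**The endpoint is largely covered elsewhere.** This stands. A reader might infer from the by-visit tables that the incidence of ECG abnormalities is not produced at all. The documents do not support that: the QT and QTcF criteria, the TEAE tables and the AESI table each supply part of it, as Step 1 shows.

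**Baseline can be seen.** SAP 3.3.9 has a Baseline rule for ECG interpretation, which suggests that the tables carry a Baseline row. With persistent abnormalities and complete data, the visit count minus the Baseline count would equal the number of new abnormalities. This fails because the Baseline row would use the best tracing and later rows the worst (Step 4). Nor does a row of totals link patients over time.

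**The numbers are assumed, and randomization balances the arms in expectation.** Both stand. A reader might infer that the summary is biased toward a false difference. It is not: with equal new-onset rates the arms are equal in expectation, and a false difference arises only from chance imbalance in a single trial.

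**Nothing is decided on this table.** Safety is descriptive, hypothesis tests are confined to efficacy, and all ECG data are listed, so old and new findings can be separated patient by patient. This limits the weight of the point. But a listing does not replace a tabulation of a named secondary endpoint, and the SAP already does this for laboratory values.

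**Conclusion.** The point holds for ECG interpretations only. The plan reports how many patients are abnormal at each visit. It does not report how many became abnormal, so new findings outside the adverse event tables and the QT and QTcF criteria cannot be separated from pre-dose ones in any planned table.

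The main consequence is dilution of any real difference in new abnormalities, with noise from Baseline imbalance added. Under the assumed rates, a 12-point difference falls to between 7.2 and 9.6 points, and from about 1.6 to 1.8 standard errors to about 0.7 to 1.0. These sizes rest on assumed Baseline prevalence (20% to 40%), assumed new-onset rates, and abnormalities that persist once present. With few patients abnormal at Baseline the loss would be small. No efficacy conclusion is affected. This is a cheap improvement to the SAP and does not invalidate the safety plan.

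**What to change.** 1. In SAP 3.3.8 and 5.5.3, define a treatment-emergent abnormal ECG interpretation as normal at Baseline and abnormal at any post-baseline assessment. Add the step from not clinically significant to clinically significant only for a reader whose data record that grade; the documents do not say that the central reading does.
2. In SAP 3.3.9, use the same triplicate-selection rule at Baseline and after Baseline for this derivation. Without this, step 1 would create apparent new abnormalities in both arms.
3. Report the number and percent of patients at risk with such an abnormality, by arm, separately for the investigator and central readings.
4. Add a shift table of Baseline by worst post-baseline interpretation for each reader. Keep the two by-visit tables as descriptive.

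The normal/abnormal derivation needs no new data collection. The cost is a little more programming, smaller denominators, and a change to the stated best/worst triplicate rule for this output.
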